The following clinical secondary outcomes are of interest: 1) percent alive and out of the hospital at Day 14; 2) change in NEW score at Day 3; and 3) resumption of normal activities at Day 14. It is expected that IVIG will have a favorable effect on each of these outcomes as well as the ordinal primary outcome. Since the primary endpoint and these secondary endpoints are related and expected to be correlated, before examining each secondary endpoint separately, a single global test will be carried out using the method described by O'Brien and Pocock. ^{45,46} With this approach, the endpoints will be equally weighted and a single global test statistic will be determined. This single global test is expected to have greater power than the test for each endpoint separately. For example, for a common correlation among the four outcomes of 0.50, the average Z value must be 1.55 (instead of 1.96) to achieve a significance level of 0.05. The combined evidence using all four outcomes does not have to be as extreme as for a single outcome.

Time to death and time to hospital discharge will be summarized with Kaplan-Meier plots and Cox models. For time-to-event analyses, time will be measured from randomization. The comparison of NEW scores and HAI titers will be compared using analysis of covariance with the baseline score or titer as a covariate. HAI titer levels will be log-transformed and the data at each time point will be summarized as the ratio of geometric means for those assigned IVIG and placebo.

Longitudinal random effects models will also be used to summarize repeated assessments of the ordinal outcome, HAI titers and the NEW score. By collecting specific dates when patients are removed from the ICU and oxygen, discharged and resume normal activities, the ordinal outcome can be defined for a patient on each day of follow-up.

Symptoms reported and AEs will be compared for the IVIG and placebo groups and summarized using chi-square statistics. Laboratory measurements will be summarized as changes from baseline to Day 7.

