Statistical Data Analysis Plan

**Anti-influenza Hyperimmune Intravenous Immunoglobulin Clinical Outcomes
Study (INSIGHT 006: FLU-IVIG)**

August 17, 2018

I. INTRODUCTION

A. Background and objective of data analysis plan

This data analysis plan (DAP) is intended to provide a description of the general analytic strategy and the statistical methods that will be used to compare the IVIG group with the placebo group of INSIGHT 006 (FLU-IVIG) upon completion of the trial.

For the initial sample size estimation as described in the protocol, category percentages for the control group for the primary 6-category ordinal endpoint at day 7 were obtained using data from the INSIGHT FLU 003 study.^{1,2} The protocol team carried out a sample size re-estimation using the pooled (both treatment groups combined) day 7 outcome data in August 2017. At that time, day 7 outcome data were available for 170 of the planned 320 participants. The pooled category percentages for the primary ordinal outcome were similar to those used from FLU 003 in the design of FLU-IVIG and power for detecting an odds ratio of 1.77, as specified in the protocol, remained 0.80. Considering this, the low percentage of participants with missing data at day 7, and the low percentage of participants who were not infused following randomization, no change to the planned sample size of 320 participants was made.

At the end of April 2018 the protocol team decided to stop enrollment on June 1, 2018 because the targeted enrollment had been achieved. The last participant enrolled in the FLU IVIG trial was on May 28, 2018 bringing the total to 313. The FLU-IVIG protocol stipulated that the 16 participants from the INSIGHT IVIG pilot trial (FLU 005)³ who met the eligibility criteria for the FLU-IVIG trial would be included in the final analysis. Thus, a total of 329 randomized participants will be considered for the primary analysis.

[figure not shown]
The analysis plan described below was prepared by blinded statisticians on the protocol team and the protocol co-chairs. It is similar to the one stated in the protocol with the following exceptions:

- The analysis set both for the primary analysis and for sensitivity analyses are defined.

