- The subgroup of participants with influenza A infection is identified as a key subgroup for whom the benefit is expected to exceed that of the overall group randomized (i.e., the treatment effect for those with influenza A is expected to be greater than for with influenza B infection) (see section C.). Power is estimated for the subgroup with influenza A.
- Outcomes other than the primary endpoint are divided into key secondary endpoints, supportive efficacy endpoints, and safety endpoints. The three key secondary endpoints are listed in terms of their importance.

B. Protocol summary and history

FLU-IVIG is a randomized, double blind multicenter, international clinical trial. Hospitalized patients with a National Early Warning (NEW) score of 2 or greater will be randomized in a 1:1 allocation ratio to either IVIG plus standard of care (SOC) therapy or to placebo for IVIG (a comparable volume of normal saline) plus SOC, and followed for 28 days. A total of 320 adult patients were to be enrolled over multiple influenza seasons. A schematic of the design is given below.

FLU-IVIG Design
Hospitalized Adults with Influenza A or B

The primary endpoint is an ordinal outcome at Day 7 that has 6 mutually exclusive categories:

1. Death
2. In the intensive care unit (ICU);
3. Non-ICU hospitalization, requiring supplemental oxygen;
4. Non-ICU hospitalization, not requiring supplemental oxygen;
5. Discharged, but unable to resume normal activities; or
6. Discharged with full resumption of normal activities.

Sample size was estimated assuming the following:

- A proportional odds model would be used to compare the IVIG and placebo groups for the primary ordinal outcome.⁴
- Type 1 error of 0.05 (2-sided) and power=0.80 to detect an odds ratio of 1.77 (an odds ratio greater than 1.0 corresponds to a more favorable response to IVIG than placebo).

For the primary analysis, in addition to a treatment indicator, the model will include indicators for whether the participant was enrolled in the ICU or general ward and whether oxygen was required, and will be stratified by geographic region.

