- If central laboratory results are negative or indeterminate for influenza strain/subtype, the local laboratory result will be used for classifying strain/subtype.
- Influenza vaccination was recorded differently on different versions of the baseline case report form. Participants will be considered as vaccinated if they report being vaccinated in the past 6 months or report being vaccinated in the season of their enrollment.
- IVIG lot will be imputed for participants assigned to placebo using the lot of the closest (in time) enrolled participant who received IVIG at that site.
- For the risk score for hospitalization or death at day 7, the following baseline covariates will be considered: age, gender, race/ethnicity, geographic region, duration of symptoms prior to enrollment, status at enrollment (ICU, general ward on O₂, general ward not on O₂), vaccination in current season, influenza strain, comorbidities (see above), other conditions (see above), and season of enrollment. The score for each participant will be determined using a logistic model that includes participants from both treatment groups.

The interaction between each subgroup and treatment will be assessed with expanded proportional odds models. Terms for each subgroup and a cross-product term with treatment will be added to the proportional odds model described above for the primary analysis. Interaction p-values for age, duration of symptoms, risk score for hospitalization or death at day 7, and NEW score will be based on the measured variable (1 df) not the categorical variable.

G. Secondary Endpoints

Some new secondary efficacy endpoints were defined, some in the protocol were dropped, and some are now defined as supportive. Reasons for this are:

- Approximately 40% of participants were discharged by day 3.
- The NEW score at day 3 was only determined for hospitalized participants. Thus, measuring change in NEW score at day 3 (as originally defined in the

protocol) is potentially biased due to missing data.

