- The NEW score encompasses several factors that have been included as outcomes in recent influenza trials (e.g., normalization of respiratory rate and oxygen saturation, or clinical stability/clinical resolution that also considers temperature, heart rate, and systolic blood pressure).^{5,6,7} Considering this and the large number of participants discharged in the first 3 days, a second ordinal outcome with 5 categories was defined based on day 3 outcomes that includes the NEW score and does not consider whether participants discharged have resumed normal activities. The latter change was made because the outcome is assessed at day 3, shortly after the acute illness, when resumption of normal activities is less likely. The categorization by the participant of resumption of normal activities was also the most subjective component of the primary ordinal endpoint.

Key Secondary Endpoints

These 3 key secondary outcomes and the supportive efficacy outcomes will be used to compare all randomized participants in the primary analysis set of participants (see D. for definition) and in those with influenza A infection who are in the primary analysis set.

- Five category ordinal outcome on day 3:
 - Death
 - ICU
 - Non-ICU hospitalization, NEW score ≥ 3
 - Non-ICU hospitalization, NEW score < 3
 - Discharged
- Primary 6-category ordinal outcome on day 3
- Favorable outcome at day 7 taking in to account enrollment from the ICU or general ward (also referred to as a sliding dichotomy⁸) defined as:
 - ICU at enrollment to general ward or discharge before day 7
 - General ward at enrollment to discharge before day 7

Power Considerations for the Key Secondary Endpoints:

- For the 5-category ordinal outcome at day 3, an odds ratio of 1.78 can be detected with power = 0.80 at the 0.05 level of significance (2-sided).
- For the 6-category primary ordinal outcome at day 3, power is 0.80 to detect an odds ratio of 1.78.
- For the favorable outcome at day 7, power is 0.80 to detect a 12.5% absolute difference in the percentage with a favorable outcome at day 7 (86% versus 73.5%). For both treatment groups combined, approximately 80% have a favorable outcome at day 7.

The percentage of participants in the 5- and 6-category ordinal outcomes described above and that are basis for power estimates are given in Table 5 for both treatment groups combined as of May 23, 2018.

Table 5

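### The SAP drops or demotes all three secondary components of the protocol's global test without redefining or withdrawing that test, and gives its new key secondaries no testing rule

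*SAP*

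**What the plan says.** Protocol 6.1 names three clinical secondary outcomes: alive and out of hospital at Day 14, change in NEW score at Day 3, and normal activities resumed at Day 14. It adds the primary ordinal outcome, making four, and states that "before examining each secondary endpoint separately, a single global test will be carried out". It also fixes the form: "the endpoints will be equally weighted and a single global test statistic will be determined". The reason given is greater power than any one endpoint has alone. The worked example uses a common correlation of 0.50 and an average Z of 1.55.

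SAP section I.A says of its own plan: "It is similar to the one stated in the protocol with the following exceptions". Three exceptions follow: the analysis sets, the influenza A subgroup, and the new endpoint tiers. On the tiers it adds: "The three key secondary endpoints are listed in terms of their importance".

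SAP section G reports that "Some new secondary efficacy endpoints were defined, some in the protocol were dropped, and some are now defined as supportive". Its key secondaries are a 5-category ordinal outcome at day 3, the 6-category ordinal outcome at day 3, and a favorable outcome at day 7 (a sliding dichotomy). Section G continues: "These 3 key secondary outcomes and the supportive efficacy outcomes will be used to compare all randomized participants in the primary analysis set", and the same comparisons are made in the influenza A participants of that set. The analysis text for the key secondaries gives a separate model for each outcome and nothing that joins them.

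**The concern.** The protocol commits to a specific procedure and the SAP changes the endpoints it is built on. A reader holding both documents would assume that the global test still stands, because the SAP presents itself as the protocol's plan plus listed exceptions and this is not one of them. Yet the analyst has no statement of whether to run the test, on which outcomes, or what its result means for the key secondaries.

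Two things are at stake. First, a planned test disappears without a declared reason, and it is one the protocol itself expects to be more powerful than any single endpoint. Second, three ranked endpoints in two populations give six comparisons with no stated rule for which may be claimed. After unblinding, any choice of rule is open to the charge that it followed the results.

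**Working it through.** **1. Components side by side.**

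| Global test component (Protocol 6.1) | Status in the SAP |
|---|---|
| Day 7 ordinal outcome | Primary (section E) |
| NEW score change, Day 3 | Dropped as potentially biased by missing data; the NEW score now enters the 5-category day 3 outcome (G) |
| Alive and out of hospital, Day 14 | Supportive (H) |
| Normal activities resumed, Day 14 | Supportive (H) |

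None of the three secondary components is a key secondary in the SAP. None of the three key secondaries was in the global test.

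**2. The protocol's own figure.** The critical average Z for k outcomes with common correlation ρ is 1.96 × √[(1 + (k − 1)ρ)/k]. With k = 4 and ρ = 0.50 this is 1.96 × √(2.5/4) = 1.55, as stated.

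For power, suppose all four outcomes carry the design effect (expected Z of 2.8, which is 80% power singly). The global test then has power Φ(2.8/√0.625 − 1.96) = 94% at ρ = 0.5. At ρ = 0.7 the variance term is 3.1/4 = 0.775 and power is 89%. This describes the protocol's four outcomes, not the SAP's new ones.

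**3. What level does the SAP use for the key secondaries?** No testing rule is given, so the level has to be read from the power statements in section G.

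- *Day 3, 5 categories.* Two-sided 0.05 is stated. Whitehead's formula gives power Φ(√[N(1 − Σp³)/12] × ln OR − 1.96). From Table 5, Σp³ = 0.119. With N = 324 and OR 1.78, power is Φ(2.81 − 1.96) = 0.80, as stated.
- *Day 3, 6 categories.* Two-sided 0.05 is stated in the summary after Table 5. Σp³ = 0.079. Power is 0.82 at N = 324 and 0.80 at N = 308, against 0.80 stated.
- *Favorable outcome, 86% versus 73.5%.* No level is stated. With 162 per group (324 assumed), a two-proportion test has power Φ{[0.125√162 − 1.96 × 0.568]/0.561} = 0.80 at 0.05, as stated. At 0.05/3 it would be 0.66. The stated power therefore implies an unadjusted 0.05.
- *Influenza A versions.* No level and no power are stated.

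**4. Error rate if each is read at an unadjusted 0.05, all nulls true.** Three independent tests would give 1 − 0.95³ = 14.3%. The outcomes are correlated, so Z statistics were simulated as multivariate normal (500,000 to 1,000,000 draws). Influenza A was nested as 232 of 308, the SAP's assumed count over its analysis set. The correlations are assumptions.

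| Assumed correlation | 3 tests | 6 tests |
|---|---|---|
| Common 0.3 | 13.7% | 19.5% |
| Common 0.5 | 12.5% | 17.8% |
| Common 0.8 | 9.8% | 14.0% |
| Day 3 pair 0.7-0.9; either with day 7, 0.4-0.6 | 10.4-12.3% | 14.9-17.5% |

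If every pair were correlated at 0.9, including day 3 with day 7, the figures would fall to 8.3% and 12.0%.

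**5. What the existing order could do.** In a fixed sequence, each at 0.05 and stopping at the first failure, a false claim requires rejecting the first true null in the sequence. That has probability at most 5%. If the primary must be significant first, the bound covers the primary and the three key secondaries together.

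**The case against.** The strongest reply concerns what the protocol promised. A reader might infer that the SAP removed a significance gate, and with it the protocol's control of false-positive secondary claims. The text does not support that. Protocol 6.1 fixes an order, global test first, and argues from power. It never says that separate tests are allowed only if the global test is significant. On that reading the same error exposure could have existed under the protocol, and the SAP did not create it. This stands. What remains is an undeclared loss of a planned test and the absence of any stated rule.

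A reader might also infer that six tests will be claimed at 0.05. The SAP does not say so. The level comes from power statements, none exists for the influenza A versions, and the wording is of comparing and summarizing. This also stands, so the error rates are conditional on that use.

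Nor do the documents suggest that the endpoint changes were hidden. The new tiers are a listed exception, section G gives reasons, and blinded statisticians and the protocol co-chairs prepared the plan. Only the loss of the global test goes unmentioned.

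Finally, one part of SAP section E, on the primary analysis, was not available for this check, and the day 3 ordinal outcomes follow the primary's plan. A relevant rule there is unlikely but cannot be excluded. Sections G and H, where such a rule belongs, contain none.

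**Conclusion.** The point holds in limited form. The protocol's global test cannot be run as defined on the SAP's secondary endpoint structure, its loss is not declared, and the ranking of the key secondaries has no function in testing. If each key secondary is read at an unadjusted 0.05, the chance of at least one false positive under the complete null is about 10-14% for three tests and 14-20% for six. Those ranges assume common correlations of 0.3-0.8, or a Day 3 pair as high as 0.9 with weaker links to day 7. They would be somewhat lower only if all three outcomes were almost interchangeable. The six-test figure also assumes 232 influenza A participants among 308. The primary analysis is not affected, so this should be corrected but does not threaten the main result.

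**What to change.** In SAP section I.A, add withdrawal of the Protocol 6.1 global test to the listed departures, with the reason that its components were changed.

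In SAP section G, turn the existing order of importance into a fixed sequence. Test the three key secondaries formally, in the full analysis set, only if the primary is significant. Take them in the listed order, each at two-sided 0.05, and stop at the first non-significant result. State where the main secondary objective of section C (the Day 7 ordinal outcome in influenza A) sits relative to this sequence. Report the influenza A versions of the key secondaries, and everything after the stop, as estimates with confidence intervals labelled unadjusted and descriptive.

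Rebuilding the global test on the new endpoints is not needed for error control. It would weight day 3 and day 7 status twice each through overlapping outcomes, and without a condition on the primary it could allow secondary claims after a failed primary.

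The cost is SAP wording, with no new data and no change to the primary analysis. The change should be made before unblinding. The downside is that some key secondaries may be reportable only descriptively.

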3.4 Endpoints

The primary endpoint is an ordinal outcome at Day 7 that has 6 mutually exclusive categories:

- 1. death;
- 2. hospitalization in the intensive care unit (ICU);
- 3. non-ICU hospitalizion, requiring supplemental oxygen;
- 4. non-ICU hospitalization, not requiring supplemental oxygen;
- 5. not hospitalized, but unable to resume normal activities; or
- 6. not hospitalized with full resumption of normal activities.

Other endpoints include:

- Change from baseline to Day 3 in NEW score
- The ordinal primary outcome assessed at Days 1-7, 14 and 28
- Number of days hospitalized
- Composite of mortality or hospitalization at Days 7, 14 and 28
- Among those not enrolled in the ICU, requirement for invasive mechanical ventilation or admission to the ICU
- Percent of patients shedding virus at Day 3
- HAI antibody titer changes through Day 7
- Grade 3 and 4 adverse events
- Serious adverse events
- Percent of patients developing bronchitis, pneumonia or other complications through Day 28
- Mortality

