3.5 Randomization

Eligible patients will be randomized in a 1:1 ratio to receive either IVIG + SOC or placebo + SOC. Randomization will be stratified by clinical site.

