Outcome at Day 7	Participants with Influenza A; Assumed Percentages in Each Category	
	IVIG (N=116)	Placebo (N=116)
Death	1.0	1.8
ICU (for FLU 003, assumed those ventilated were in the ICU)	1.9	3.6
Non-ICU hospitalization, O ₂	9.1	15.6
Non-ICU hospitalization, no O ₂	9.7	14.1
Discharged, not back to normal activities	37.8	39.0
Discharged, back to normal activities	40.5	25.8

D. Analysis Set

The analysis set for the primary efficacy and safety analyses and all other analyses will exclude 21 randomized participants:

- 4 participants who declined to receive an IVIG/placebo infusion; and
- 17 participants at a single site in Thailand for whom eligibility based on the NEW score could not be confirmed and data alteration of the vital signs used to compute the NEW score was suspected.

One other participant (at a different site) did not meet strict eligibility criteria. This participant had a locally determined positive influenza test 4 days prior to randomization instead of within 2 days as stated in the protocol. This participant will be retained in the

primary analysis because this was not considered to be major, there was no evidence that it was intentional, and it is in keeping with the intention to treat principle. Thus, analyses in the final report will be restricted to 308 randomized participants. These analyses will be referred to as modified intention to treat.

For the primary efficacy analysis, missing day 7 outcomes (4 participants have missing outcomes among those infused) will be imputed for participants who were infused.

Sensitivity analyses will be carried out to assess the impact of including participants from the pilot study, to assess the impact of imputation for the primary outcome, and to assess the impact of the exclusion of participants from the site in Thailand.

The four sensitivity analyses are:

- 1) An analysis that excludes participants enrolled in the IVIG pilot (16 participants).
- 2) An analysis that excludes participants for whom the day 7 outcome is missing (4 participants).
- 3) An analysis that includes the 17 participants who may not have met the NEW score eligibility criteria at the site in Thailand.
- 4) An analysis that excludes all participants at the site in Thailand (80 total) for which the eligibility of 17 participants could not be confirmed.

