To supplement the overall summary odds ratio, separate odds ratios will be estimated for each dichotomized definition of improvement that can be formulated from the components of the ordinal outcome. A test for the proportionality assumption will also be made.

Analyses identical to those described above (including the imputation) will be carried out for participants with influenza A virus infection. If the central determination of influenza resulted in negative or indeterminate results, the local determination will be used. For participants with a co-infection with A and B influenza subtypes, the participant will be classified as A.

The analyses described above will be carried out for the primary efficacy analysis and for the two planned sensitivity analyses.

These analyses will be supplemented with summaries which give the category percentages for the primary ordinal outcome by treatment group for days 1-7.

F. Subgroup Analysis

Analyses will be carried out for the following baseline-defined subgroups:

- Influenza strain (A, B) and subtype (pH1N1, H3N2, B)
- Age (<40, 40-59, ≥ 60 years)
- Gender (men, women)
- Race/ethnicity (White/Hispanic/other, Black, Asian)
- Enrollment ward/use of O₂ (ICU, general ward on O₂, general ward not on O₂)
- Geographic region (United States/South America/Mexico, Europe/Australia, Thailand)
- Northern/Southern hemisphere/Equatorial (United States, Mexico, and Europe vs Australia and South America vs Thailand)
- Duration of symptoms prior to randomization (≤ 3, 4, ≥ 5 days)
- New score (≤ 3, 4-5, ≥ 6)
- Influenza season (Oct2013-Sep2014, Oct2014-Sep2015, Oct2015-Sep2016, Oct2016-Sep2017, Oct2017-Jun2018)
- Co-morbidities (CVD, COPD/asthma, diabetes, none of these) (as hierarchy)
- Other conditions (sepsis, pneumonia, immune suppression) (each considered separately versus not having the condition)

- Influenza strain/viral load (A and viral load > 100,000/≤ 100,000, B and viral load > 1,000,000/≤ 1,000,000) (4 categories)
- Influenza vaccination (yes, no, unknown)
- Smoking status (current smoker, non-smoker)
- IVIG lot (1-5)
- HAI titer (highest titer measured)
- HAI titer corresponding to subtype of infection (highest titer measured)
- Risk score tertile for hospitalization or death at day 7

The following special situations will apply to the categorization of participants for subgroup analyses:

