If a NEW score is not available on Day 3, the last available follow-up NEW score will be used.

For the favorable outcome on Day 7, for the 4 participants who are missing the primary outcome on Day 7, it is presumed that they did not die or were re-hospitalized following discharge, i.e., they will be considered as having a favorable outcome.

H. Supportive Efficacy Endpoints

The following efficacy outcomes are defined as supportive:

- Time to discharge
- Time to death
- Percentage alive and out of the hospital at day 28
- Change in nasopharyngeal viral load from baseline to day 3
- Change in HAI titers from baseline to day 1, 3 and 7
- Percentage dying or requiring re-hospitalization after discharge
- Percentage with a diagnosis on or after the day of randomization and before the day 28 visit developing acute respiratory distress syndrome, acute renal failure, sepsis, pneumonia, enteritis or bronchitis (considered individually and also any of the diagnoses)
- Ordinal outcome on day 14
- Percentage alive and out of the hospital at day 14
- Resumption of normal activities at day 14.
- Ordinal outcome on day 28

Analysis Considerations for Supportive Efficacy Outcomes

Kaplan-Meier curves will be used to summarize the time to discharge and time to death, overall and through 7 days. The median number of days from randomization to discharge will be estimated. Deaths during hospitalization will be censored after day 28 (or day 7) for analyses of time to discharge. A logrank test will be used to compare treatment groups.

For participants who experienced multiple hospitalizations during follow-up, the time to the last discharge before day 28 will be considered. As the visit window for the day 28 visit extends to day 35, events after day 28 but prior to the final visit will be included in these analyses.

The difference between the IVIG and placebo group for change in log-transformed nasopharyngeal viral load from baseline to day 3 will be summarized using stratified analysis of variance with baseline viral load as a covariate. Viral loads vary by subtype. Therefore, strata will be defined by influenza virus subtype (H1N1, H3N2, or B) as well as geographic region. In these analyses, levels below 75 copies, the lower limit of detection, will be imputed as 75 copies. For this analysis, deaths (currently one

participant) on or before day 3 will be excluded, as will participants with undetectable RNA.

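### SAP H dates complications from the day of randomization with no rule for diagnoses already present, so a presenting illness dated Day 0 can be scored as an outcome

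*SAP*

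**What the plan says.** Protocol section 3.4 lists the endpoint as "Percent of patients developing bronchitis, pneumonia or other complications through Day 28". SAP section H makes it operational through a date window: "Percentage with a diagnosis on or after the day of randomization and before the day 28 visit developing" ARDS, followed by "acute renal failure, sepsis, pneumonia, enteritis or bronchitis (considered individually and also any of the diagnoses". The window opens on Day 0 itself.

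The population comes from SAP section G, where the key secondary and "supportive efficacy outcomes will be used to compare all randomized participants in the primary analysis set of participants", and also those in that set with influenza A. Section D fixes its size: "analyses in the final report will be restricted to 308 randomized participants". For binary outcomes, section H specifies a logistic model stratified by region, with terms for ward and oxygen status at entry and for pilot membership. There is no term for a complication present at entry and no restriction to participants at risk.

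Two of the six components also appear on the baseline side. The baseline-defined subgroups in SAP section F include "Other conditions (sepsis, pneumonia, immune suppression) (each considered separately versus not having the condition", and section J lists complications among the baseline tabulations.

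**The concern.** Participants are inpatients with influenza and a NEW score of at least 2. Under Protocol section 3.9.1, screening work-up may fall on any day from Day -2 to Day 0. Under section 3.9.3 the infusion follows randomization on Day 0, and SAP section K allows for it starting on the next day or later. A pneumonia or sepsis recognised on Day 0 before randomization meets the section H date rule, and the same patient can be a baseline case in section F.

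Such a diagnosis cannot respond to treatment. Counted in both arms, it raises the reported complication rate and moves the odds ratio toward 1, so the endpoint departs from the new-onset question in the protocol.

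The documents take more care with comparable outcomes. Protocol section 3.4 limits ICU admission or ventilation to those not enrolled in the ICU. Protocol section 4.2.5 limits adverse event collection to new or worsened grade 3 or 4 events. SAP section H adjusts viral load and HAI titer for baseline.

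**Working it through.** **No figure to reproduce.** The documents give no event rate, effect size or power for this endpoint. As a check of method I used the nearest binary endpoint, the favorable Day 7 outcome in SAP section G (86% v 73.5%, stated power 0.80). The formula below gives 0.802 with 324 participants and 0.782 with 308, so it agrees with the SAP.

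**Inputs from the documents**
- Analysis set: 313 + 16 = 329; 329 - 21 = 308 (SAP sections A and D).
- Allocation: "Eligible patients will be randomized in a 1:1 ratio to receive either IVIG + SOC or placebo + SOC", so about 308/2 = 154 per arm. The actual split is not stated.
- Two-sided alpha of 0.05, stated for the primary outcome and borrowed here.

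**Assumptions, not in the documents**
- New-onset risk among those at risk: p = 0.20 on placebo and 0.10 on IVIG.
- q = share of each arm with the complication already present at entry.

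**Formulas**
- Prevalent cases dated Day 0 and counted: observed risk = q + (1 - q)p, with n = 154.
- Prevalent cases dated before Day 0, so not events but kept in the denominator: observed risk = (1 - q)p, with n = 154.
- Prevalent cases excluded: risk = p, with n = 154(1 - q).
- Power = Φ[(d - 1.96·SE0)/SE1], where d is the risk difference, SE0 the pooled and SE1 the unpooled standard error. This is unadjusted and without continuity correction.

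**Worked line, q = 0.10, counted.** Placebo 0.10 + 0.90 × 0.20 = 0.28. IVIG 0.10 + 0.90 × 0.10 = 0.19. Odds ratio (0.19/0.81)/(0.28/0.72) = 0.60. SE0 = √(0.235 × 0.765 × 2/154) = 0.0483 and SE1 = √((0.28 × 0.72 + 0.19 × 0.81)/154) = 0.0480. Power = Φ[(0.09 - 1.96 × 0.0483)/0.0480] = 0.46.

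| q | Counted: rates | OR | Power | Kept, not counted: OR | Power | Excluded: n per arm | Power (OR 0.44) |
|---|---|---|---|---|---|---|---|
| 0 | 20.0% v 10.0% | 0.44 | 0.692 | 0.44 | 0.692 | 154 | 0.692 |
| 2% | 21.6% v 11.8% | 0.49 | 0.636 | 0.45 | 0.682 | 150.9 | 0.684 |
| 5% | 24.0% v 14.5% | 0.54 | 0.562 | 0.45 | 0.666 | 146.3 | 0.670 |
| 10% | 28.0% v 19.0% | 0.60 | 0.461 | 0.45 | 0.638 | 138.6 | 0.646 |
| 20% | 36.0% v 28.0% | 0.69 | 0.324 | 0.46 | 0.580 | 123.2 | 0.595 |
| 30% | 44.0% v 37.0% | 0.75 | 0.239 | 0.46 | 0.518 | 107.8 | 0.539 |

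The counted columns assume that every prevalent case carries a Day 0 date, so they are an upper limit for each q. If only a quarter of prevalent cases are dated Day 0 (a further assumption), the results are:
- q = 10%: rates 0.025 + 0.18 = 20.5% v 0.025 + 0.09 = 11.5%, odds ratio 0.50, power 0.58.
- q = 20%: rates 0.05 + 0.16 = 21.0% v 0.05 + 0.08 = 13.0%, odds ratio 0.56, power 0.46.

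Other assumed rates show the same pattern. At 15% v 7.5% (odds ratio 0.46), q of 5% and 10% counted gives odds ratios of 0.58 and 0.65 and power of 0.40 and 0.31, against 0.53 and 0.51 with those cases excluded.

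**The case against.** The strongest reply is that both documents use the word *developing*, which points to new onset, and that a diagnosis dated before Day 0 is not an event. No document shows that a condition recorded at baseline is entered again as a follow-up diagnosis, and the Protocol Instructions Manual may settle it. This stands as far as it goes: a reader might infer that every Day 0 diagnosis, including all presenting illness, will be counted, and the text does not establish that. But the date is the only operational criterion in section H, and a programmer who follows it will count a Day 0 diagnosis.

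A reader might also infer that keeping patients with earlier-dated complications in the denominator dilutes the effect. It shrinks the risk difference, but the risk ratio is unchanged, the odds ratio moves only from 0.44 to 0.45-0.46, and the power cost against exclusion is at most about 2 points (0.518 v 0.539 at q = 30%). That half carries little weight on its own.

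Finally, this is one of eleven supportive endpoints and has no power claim. With randomized, blinded arms, diagnoses made before randomization should balance. The risk is lost sensitivity and an inflated rate; nothing here points to a false-positive result.

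**Conclusion.** The point holds in a limited form. As written, the section H rule allows a complication present before randomization but dated Day 0 to be scored as an outcome, and neither the population nor the model corrects for it. This is more than a missing detail, because a literal date rule is given and two components are also baseline conditions.

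The size cannot be stated, since prevalence at entry, the share dated Day 0 and the event rates are all absent. Under the assumed 20% v 10%, even 2% of each arm counted in this way costs about 5 points of power (0.636 v 0.684), and 10% costs about 18 points (0.461 v 0.646). It would go too far to conclude that any IVIG effect will be diluted: if few presenting diagnoses carry a Day 0 date, the loss is small. The primary and key secondary analyses are unaffected.

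**What to change.** In SAP section H, count a diagnosis as an event only if it is first made after randomization and was not recorded as present at baseline. State that a Day 0 diagnosis also recorded as a baseline condition is not an event. Report each component among participants free of it at baseline wherever baseline data exist. Sepsis and pneumonia are named in section F; whether the baseline complications in section J cover ARDS, acute renal failure, enteritis and bronchitis has to be confirmed. Keep the present all-participant version, counted from Day 0, as a sensitivity analysis.

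Randomization should stay as time zero, in line with Protocol section 6.1. Starting at infusion would drop events after randomization in participants infused late. Starting at Day 1 would discard true Day 0 events, including acute renal failure, which Protocol section 2.4.1 lists as a possible IVIG risk.

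The cost is a few lines of SAP text and a short program change, slightly smaller denominators per component, and some remaining uncertainty for Day 0 diagnoses with no recorded time. No new data are needed for sepsis and pneumonia if the section F subgroups are built from baseline records.
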